## 6.2 Safety Variables

- AEs
- Vital signs (body temperature, pulse rate and blood pressure in sitting position)
- Body weight
- Central ECG
- 12-lead ECG
- Central electrocardiogram
- Chest radiography
- Laboratory assessments

**Treatment emergent adverse events** (TEAEs) will be defined as any adverse event that started or worsened in severity after initial dose of study drug through Week52 or Withdrawal.

AE for the subjects who switched ASP015K 100 mg or ASP150 mg from Placebo at Week 12 or Week 28 will be handled as follows.

- AE onset before the first dose of week12 study drug will be considered to be occurred at Placebo.
- AE onset after the first dose of week12 study drug before the first dose of week28 study drug will be considered to be occurred at Placebo if the subject did not switch Placebo at Week 12. Else, if the subject switched ASP015K 100 mg or 150 mg at Week12, then the AE onset after the first dose of week12 study drug before the first dose of week28 study drug will be considered to be occurred at ASP015K 100 mg or 150 mg.
- AE onset after the first dose of week28 study drug will be considered to be occurred at ASP015K 100 mg or 150 mg, which is switched treatment from Placebo.

A drug-related TEAE is defined as any TEAE with possible, probable or missing relationship to study drug as assessed by the investigator. Moreover, any TEAE with missing relationship to study drug or reference drug was counted as drug related (probable).

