SEQ2	150mg	ASP015K 150 mg	ASP015K 150 mg	ASP015K 150 mg	
SEQ3	Placebo to 100mg at Week 12	Placebo	ASP015K 100 mg	ASP015K 100 mg	
SEQ4	Placebo to 150mg at Week 12	Placebo	ASP015K 150 mg	ASP015K 150 mg	
SEQ5	Placebo to 100mg at Week 28	Placebo	Placebo	ASP015K 100 mg	
SEQ6	Placebo to 150mg at Week 28	Placebo	Placebo	ASP015K 150 mg	

- 100 mg: subjects who initially treated ASP015K 100 mg
- 150 mg: subjects who initially treated ASP015K 150 mg

- Placebo to 100 mg at Week 12: subjects who initially treated Placebo group and switched 100 mg at Week 12 and at least one dose of ASP015K 100 mg drug after switched
  - Placebo to 150 mg at Week 12: subjects who initially treated Placebo group and switched ASP015K 150 mg at Week 12 and at least one dose of ASP015K 150 mg drug after switched
  - Placebo to 100 mg at Week 28: subjects who initially treated Placebo group and switched ASP015K 100 mg at Week 28 and at least one dose of ASP015K 100 mg drug after switched
  - Placebo to 150 mg at Week 28: subjects who initially treated Placebo group and switched ASP015K 150 mg at Week 28 and at least one dose of ASP015K 150 mg drug after switched
- 
- The analyses for mTSS (Appendix 1, Appendix 2), erosion score, and joint space narrowing score will be performed at Week 28/ET and Week 52/ET, and statistical testing will also be conducted at Week 28/ET, Week 52/ET, compared with Placebo. These analyses include primary analysis (mTSS change from baseline at Week 28/ET).
  - MedDRA 11.1 will be used as the coding dictionary for adverse event and medical history.
  - Statistical hypothesis testing will be performed only if specified. All statistical comparisons of treatment groups will be versus placebo (i.e., each ASP015K treatment versus placebo) and will be made using two sided tests at the 0.05 significance level, unless stated otherwise. Multiplicity adjustment will be done in the primary analysis and other analysis if specified.
  - Statistical analysis including hypothesis testing for efficacy variables to compare 100 mg or 150 mg versus Placebo, only the data for the pairwise comparison will be used.
  - All statistical results will be presented, as appropriate, by treatment group, by treatment group and scheduled visit; the schedule of assessments is provided in 7.11.4.

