## 7.5 Analysis of Safety

In general, For AE Analysis up to Week 12 will be performed by Initial Randomization Set in SAF. AE Analysis from "Week 12 to the Last Evaluation" will be performed by Treatment Sequence Set in SAF. AE 100 Patient-Years analysis will be performed by Groups for Patient-Years. Details for analysis groups will be described in 10.3 Appendix3.

For other safety analysis except for AE up to Week 12 will be performed by Initial Randomization Set in SAF. For other safety analysis except for AE up to Week 52 will be performed by Treatment Sequence Set in SAF. Details for analysis groups will be described in 10.3 and 10.4.

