### 10.3 Appendix 3: Overview of AE analysis

Table16, Table17 summarizes the analyses of AE occurrence, the analysis of SOC, PT analysis, with "X1", "X2", "X3", and "X4" indicating that the variable will be analyzed by each defined groups defined footnote. All analyses will be based on the SAF.

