**Table16. The overview of AE occurrence analysis**

	Overall	Week 0 to Week 12	Week 12 to Week 28	Week 28 to Week 52
Number and percentage of subjects with TEAE	X4	X1	X2	X3
Number and percentage of subjects with drug related TEAE	X4	X1	X2	X3
Number and percentage of subjects with death	X4	X1	X2	X3
Number and percentage of subjects with serious TEAE	X4	X1	X2	X3
Number and percentage of subjects with drug related serious TEAE	X4	X1	X2	X3
Number and percentage of subjects with TEAE Grade 3 or Higher in Severity	X4	X1	X2	X3
Number and percentage of subjects with TEAE leading to study drug discontinuation	X4	X1	X2	X3
Number and percentage of subjects with drug related TEAE leading to study drug discontinuation	X4	X1	X2	X3
Number and percentage of subjects with Serious TEAE Leading to Permanent Discontinuation of Study Drug	X4	X1	X2	X3
Number and percentage of subjects with Drug-Related Serious TEAE Leading to Permanent Discontinuation of Study Drug	X4	X1	X2	X3

X1: Placebo, 100mg, 150mg

X2: Placebo, 100mg, 150mg, Placebo to 100 mg at Week 12, Placebo to 150 mg at Week12

X3: 100mg, 150mg, Placebo to 100 mg at Week 12, Placebo to 150 mg at Week 12, Placebo to 100 mg at Week 28, Placebo to 150 mg at Week 28

X4: 100mg, 150mg

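### In the Week 12-28 and Week 28-52 adverse event tables, the 100 mg and 150 mg columns keep subjects who left before the period while the switch columns require a dose after the switch, so equal risks print as unequal percentages

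*SAP*

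**What the plan says.** SAP 7.5 states that adverse event analysis from Week 12 to the last evaluation "will be performed by Treatment Sequence Set in SAF". Appendix 3 (SAP 10.3) adds "All analyses will be based on the SAF", and SAP 5.3 admits to the SAF anyone with one dose at any time.

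SAP 7.1 defines the columns. The continuous-dose groups are "100 mg: subjects who initially treated ASP015K 100 mg" and "150 mg: subjects who initially treated ASP015K 150 mg". A Week 12 switch group needs more: "switched 100 mg at Week 12 and at least one dose of ASP015K 100 mg drug after switched". The Week 28 switch groups carry the same kind of condition, tied to the Week 28 switch.

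Tables 16 and 17 set these columns side by side. The Week 12-28 list is "X2: Placebo, 100mg, 150mg, Placebo to 100 mg at Week 12, Placebo to 150 mg at Week12". The Week 28-52 list (X3) has 100 mg, 150 mg and all four switch groups, with no Placebo column. SAP 7.5.1.1 asks for the number and percentage of subjects.

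For placebo-arm subjects, SAP 6.2 says which treatment an event is charged to. Between the Week 12 and Week 28 doses an event "will be considered to be occurred at Placebo if the subject did not switch Placebo at Week 12"; otherwise it goes to the dose switched to. That rule governs events and sets no denominator.

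**The concern.** A percentage of subjects with an event in a period means what it appears to mean only if everyone in the denominator could have had an event in that period. A 100 mg subject who left at Week 6 is still in the 100 mg sequence and in the SAF, and so remains in the Week 12-28 denominator with almost no chance of contributing an event. Every subject in a Week 12 switch column was dosed in that period. Columns printed next to each other therefore use different kinds of denominator.

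The error has one direction: the continuous-dose columns look safer than newly started treatment at the same true risk. If losses before Week 12 differ between 100 mg and 150 mg, the comparison between doses shifts as well.

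**Working it through.** **Inputs**
- N = 170 per group and about 10% dropout: SAP 4. The dropout figure is a sample-size allowance and is not stated as loss by Week 12; using it that way is an assumption.
- Discontinuation because of adverse events in the 12-week Phase IIb study: 10.9% at 100 mg and 6.9% at 150 mg (Protocol 1.3). These are used only as plausible values for early loss.
- True risk r in a period among subjects treated in it: not given in the documents. Assumed 20%, 40% and 60%.

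The plan states no denominator or incidence for these tables, so there is no figure of its own to reproduce on this point. The sample size behind N = 170 does check: for a difference of 1.5 and SD 4.0, t-test power is 0.899 at 150 per group and 0.901 at 151, which matches the stated 151.

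**Formula**

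Printed percentage = r × (subjects at risk at the start of the period ÷ column N). This takes leavers as contributing no events. The exception would be an event in the 4-week follow-up of someone who left shortly before the period began.

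**Week 12-28, worked case**
- At risk: 170 × 0.90 = 153.
- Subjects with an event: 0.40 × 153 = 61.2.
- 100 mg or 150 mg column as defined: 61.2 ÷ 170 = 36.0%.
- Week 12 switch columns: 40.0%, because every member was dosed after the switch.
- Gap: r × loss = 0.40 × 0.10 = 4.0 points.

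**Week 12-28, range: what the 100 mg or 150 mg column prints**

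| Loss before Week 12 | r = 20% | r = 40% | r = 60% |
|---|---|---|---|
| 5% | 19.0% | 38.0% | 57.0% |
| 6.9% | 18.6% | 37.2% | 55.9% |
| 10% | 18.0% | 36.0% | 54.0% |
| 10.9% | 17.8% | 35.6% | 53.5% |
| 15% | 17.0% | 34.0% | 51.0% |

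The switch columns print 20%, 40% and 60%. The gap runs from 0.20 × 0.05 = 1 point to 0.60 × 0.15 = 9 points. With the Phase IIb rates, equal 40% risks print 35.6% at 100 mg and 37.2% at 150 mg.

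**Week 28-52, r = 40%, 10% lost before Week 12**

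| Column | Further 5% lost by Week 28 | Further 10% lost by Week 28 |
|---|---|---|
| 100 mg, 150 mg | 0.40 × 0.90 × 0.95 = 34.2% | 0.40 × 0.90 × 0.90 = 32.4% |
| Week 12 switch | 0.40 × 0.95 = 38.0% | 0.40 × 0.90 = 36.0% |
| Week 28 switch | 40.0% | 40.0% |

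The Week 12 switch groups need only one dose after the Week 12 switch, so they also keep subjects lost before Week 28. Only the Week 28 switch columns are confined to subjects dosed in this period. One table thus holds three kinds of denominator.

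**Placebo column, Week 12-28**

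Placebo is not one of the six treatment sequences, so this column has no definition. Three readings are possible:
- Subjects still on placebo after Week 12: prints 40%.
- The two Week 28 switch sequences combined: leaves out anyone who stopped placebo between Weeks 12 and 28, since both require a dose after the Week 28 switch.
- All 170 initially treated, with only non-switchers' events counted: 0.40 × 0.90 × (1 − s), which is 25.2%, 18.0% or 14.4% if a share s of 30%, 50% or 60% of those remaining switch.

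**The case against.** A reader might infer that the Placebo column is the worst affected and makes placebo look far safer than it is. The documents do not support this. The only group labelled simply Placebo is in Table 3 of SAP 7.1, which is set up for efficacy, and SAP 7.5 uses that set for adverse events only up to Week 12. SAP 7.1 says safety is presented by actual treatment, and SAP 6.2 counts an event in this interval as a placebo event only for subjects who did not switch. The Week 12 switchers already have their own columns. All of this favours subjects still on placebo, so the figures of 25.2%, 18.0% and 14.4% are conditional on an unlikely reading. Nor does the problem reach a placebo column in Week 28-52, because that table has none.

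A reader might also infer that the 52-week safety objective rests on these tables. SAP 7.5.1 makes Week 0-12 the main comparison with placebo and the overall period the focus for the dose groups. The overall tables (X4) hold only 100 mg and 150 mg, so they do not mix denominators. SAP 7.1 calls the switch groups optional and outside the primary objective. Week 12 switchers are selected for inadequate response, so comparing them with the continuous arms is non-randomised whatever the denominator. These arguments stand, and they limit the importance of the point.

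Two further defences carry less weight. The TLF specifications, which are not available here, may set a period denominator; but the SAP cites them for formats, and who is at risk is an analysis decision. SAP 7.5.1.2 plans rates per 100 patient-years because of possible differential dropout, but the patient-year table in Appendix 3 lists only Week 0-12 and the overall period, and SAP 7.5.1 is ambiguous about the two later periods.

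**Conclusion.** The concern holds for the 100 mg and 150 mg columns. On the SAP's own group definitions they print lower than the Week 12 switch columns in Week 12-28, and lower than the Week 28 switch columns in Week 28-52, when the true risks are equal. In Week 12-28 the shortfall equals risk times prior loss, which is a relative understatement of about 10% at the planned dropout rate. The size rests on assumed risks, on treating the dropout allowance as loss before Week 12, and on the SAP definitions being used as denominators without a further restriction in the table specifications.

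The Week 12-28 Placebo column is a gap in definition and not a demonstrated bias. No hypothesis test or efficacy result is affected. This is worth correcting because percentages printed side by side should be comparable.

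**What to change.** In SAP 7.5 and in Appendix 3 Tables 16 and 17, define N for each period and column as SAF subjects who took at least one dose of that column's treatment in that period, and count events in the same subjects. Specifically:
- Week 12-28, 100 mg and 150 mg: initially assigned subjects dosed on or after the Week 12 dispensing.
- Week 12-28, Placebo: placebo subjects not switched at Week 12 and dosed after Week 12.
- Week 28-52, all columns, including the Week 12 switch groups: subjects dosed in that period.

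Also state whether the patient-year rates cover Week 12-28 and Week 28-52.

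In the worked case this moves the Week 12-28 dose columns from 61.2 ÷ 170 = 36.0% to 61.2 ÷ 153 = 40.0%, level with the switch columns. The cost is SAP wording and one population flag per period. The printed incidences in the dose columns become slightly less favourable.

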## 7.2 Study Population

### 7.2.1 Disposition of Subjects

The following subject data will be summarized and presented with regard to All Subjects with Screening Failure Log and Case Report Form.

- Screened
- Screen failed
- Randomized

The following subject data will be summarized and presented by Initial Randomization Set and Treatment Sequence Set:

- Subjects randomized and dosed (same as the FAS)
- Subjects who prematurely discontinued from the study period during overall period
- Subjects who prematurely discontinued from the study period by 4 weeks
- Subjects who included/excluded of FAS, PPS-ACR, PPS-MTSS, SAF, PKAS, and PDAS

- Subjects who were excluded from FAS, PPS, SAF, PKAS, and PDAS will be summarized by reason for exclusion.

The following analysis will be conducted for Initial Randomization Set.

- For time-to-withdrawal from initial dose up to Day 92: Kaplan-Meier plot will be constructed.

### **Withdrawal Due to Lack of Efficacy:**

In addition to the disposition summaries, the percentage of subject withdrawal due to lack of efficacy as the primary reason for withdrawal will be compared (each ASP015K dose group versus placebo) using Fisher's exact test, and the analysis will be based on SAF by Initial Randomization Set. Fisher's exact p-values (No multiplicity adjustment) will be provided.

The following subject data will be summarized and presented by Initial Randomization Set and Treatment Sequence Set

- Subjects who discontinued after starting the study period will be summarized for primary reason for withdrawal during overall period.
- Subjects who discontinued after starting the study period will be summarized for primary reason for withdrawal by 4 weeks.

[Analysis population: FAS]

- Subjects who applied to the improvement rate from baseline in tender/swollen joint count(68/66) less than 20% at Week12

## **7.2.2 Demographic and Other Baseline Characteristics**

All demographic and other baseline characteristics (defined below) will be summarized by treatment group. To explore the imbalance among treatment groups, comparisons with respect to categorical variables (e.g., sex) will be based on chi-squared test (continuity corrected), and comparisons with respect to continuous variables (e.g., BMI) will be based on a one-way ANOVA model with fixed effect for treatment group. All analyses/summaries except for (7.2.2.4) will be based on the SAF, FAS, and PPS.

If the imbalance of the factors between treatment groups is found (at a two-sided 0.05 significance level) and considered to clinically affect the primary variable, an analysis adjusted for the factor will be performed to assess the effect of the primary variable on the primary analysis.

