  - In addition, demographics and other baseline characteristics, and safety results will be provided for all ASP015K treatment groups combined ("ASP015K Total") and for all treatment groups, including placebo, combined ("Total"). Efficacy presentations will not contain combined treatment groups.
  - Chi-square test is continuity corrected in all analysis.
  - Confidence interval for binary outcome is continuity corrected in all analysis.
  - The values below the lower limit of quantitation (BQL) for  $\beta$ -D-glucan, hCG, Troponin, CK-MB will be treated as it is and these variables are not used for descriptive statistics and displayed in the listings. As for  $\beta$ -D-glucan, it is used for shift-from baseline analysis.
  - If anti-CCP antibody (U/mL) is beyond measurement (i.e.  $>500$  U/ml) then Anti-CCP antibody is regarded as 500 U/ml, and categorized in  $>500$  U/ml. Also, if anti-CCP antibody (U/mL) is below measurement (i.e.  $<0.6$  U/ml) then Anti-CCP antibody is regarded as 0.6 U/ml, and categorized in  $<4.5$  U/mL.

- CRP (mg/dL) is below measurement (i.e. <0.01 mg/dL) then CRP is regarded as 0.01 U/ml, and used for the calculation of DAS28-CRP, etc. and categorized in <1.0 mg/dL.
- If Rheumatoid Factor (IU/mL) is below measurement (i.e. <3 IU/mL), then Rheumatoid Factor is regarded as 3 IU/mL and categorized in <- 15 IU/ml.
- Baseline for safety is defined as last non-missing value before the first dose of study drug for all subjects including placebo assigned subjects.
- Baseline for efficacy is defined as value at Day1 before the first dose of study drug for all subjects including placebo assigned subjects.
- Change from baseline to post-baseline will be calculated as: post-baseline value - baseline value. If the baseline value is missing, then that subject is not included in the calculation at any visit.
- Percent change from baseline to post-baseline will be calculated as:  $100 \times (\text{change} / \text{baseline})$ . If the baseline value is 0 or missing, or post-baseline value is missing, then Percent change from baseline to post-baseline is missing.
- If onset date of AE is Unknown, then missing onset date of AE will be imputed as following steps.
  1. If only the day of the month is missing (e.g., 2013-03), then the first day of the month will be used (2013-03-01),
  2. If both day and month are missing (e.g., 2013), then the first day of January will be used (2013-01-01).

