**Table 1. Demographic Variables and Analysis Methods**

Item	Classification	Testing Method
Age (at the time of Informed Consent)	Measurement value	one-way ANOVA
	<65, >= 65	-
Sex	Male, Female	chi-squared test
Height (cm)	Measurement value	one-way ANOVA
Body Weight[Screening] (kg)	Measurement value	one-way ANOVA
	<- 40 kg, 40 kg <- 60 kg, 60 kg <- 80 kg, > 80 kg	-
BMI [Screening] (kg/m2)	Measurement value	one-way ANOVA
Complications	No, Yes	
Previous Medications	No, Yes	
Concomitant Medications	No, Yes	
Concomitant DMARD except for MTX at Baseline	No, Yes	chi-squared test
Concomitant Steroid at Baseline*	No, Yes	chi-squared test
Prednisone dose at Baseline (mg/day) *	Measurement value	one-way ANOVA
	None, 0 <- 5 mg/day, > 5 mg/day	

\*: Concomitant Steroid and Prednisone dose is applied for “Oral Use”.

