### 7.2.2.2 Baseline Disease Activity

The following baseline disease activity variables will be summarized by descriptive statistics, and imbalance between treatment groups will be considered based on a one-way ANOVA model with fixed effect for treatment group.

- TJC-68
- TJC-28
- SJC-66
- SJC-28
- SGAP (100 mm VAS)
- SGA (100 mm VAS)
- PGA (100 mm VAS)
- HAQ-DI (scale 0 - 3)
- CRP (mg/dL)
- ESR (mm/hr)
- DAS28-CRP
- DAS28-ESR
- SDAI score
- WPAI
- SF-36V2®

- mTSS
- Erosion Score
- Joint Space Narrowing Score
- Estimated mTSS yearly progression

Note: yearly progression from onset to baseline; baseline mTSS/ Duration of RA (years)

In addition, following baseline efficacy categorical variables will be summarized as well.

- Baseline mTSS (<=Median, > Median)
- Baseline CRP (< 1.0, >= 1.0)
- Baseline DAS28-CRP (<= 3.2, 3.2 <- 5.1, > 5.1)
- Baseline DAS28-ESR (<= 3.2, 3.2 <- 5.1, > 5.1)

All summaries will be provided separately for SAF, FAS and PPS.

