**Table 2. RA History and Analysis Methods**

Item	Classification	Testing Method
ACR 1991 Revised Criteria for Global Functional Status in RA	Class I, Class II, Class III	chi-squared test
Steinbrocker Classification	Stage I, Stage II, Stage III, Stage IV	chi-squared test
Prior Surgical Procedure to Treat RA	No, Yes	chi-squared test
Duration of RA (years)	Measurement value	one-way ANOVA
	<5 years, >= 5 years	-
	< 1 year, 1 year -<5 years, 5 years -< 10 years, >- 10 years	-
Onset Age of RA (years), calculated as: (onset date of RA – date of birth+1) / 365.25	-	one-way ANOVA
Anti-CCP Antibody (U/mL)	Measurement value	one-way ANOVA
	Low-positive or negative (<- 3 x ULN), High-positive (> 3 x	-

		ULN)	
		< 4.5 U/mL, 4.5 -< 13.5 U/mL, 13.5 -< 90 U/mL, 90 -< 180 U/mL, 180 -< 500 U/mL, >- 500 U/ml	-
Rheumatoid Factor (IU/ml)		Measurement value	one-way ANOVA
		Low-positive or negative (<- 3 x ULN), High-positive (> 3 x ULN)	-
		<- 15 IU/ml, 15 <- 45 IU/ml, 45 <- 150 IU/ml, > 150 IU/ml	-
Prior MTX	Maximum Dose	Fixed Unit: mg/week	-
	Reactivity	Response, Inadequate Response, Unknown	-
	Tolerance	Intolerance, Tolerance, Unknown	-
MTX Dose at Baseline (mg/week)		Measurement value	one-way ANOVA
		0 <- 8 mg/week, 8 <- 12 mg/week, > 12 mg/week	
		0 <- 6 mg/week, 6 <- 8 mg/week, 8 <- 10 mg/week, 10 <- 12 mg/week, 12 <- 16 mg/week, 16 <- mg/week	
Prior Non-Biologic DMARD Except for MTX	Use	Non-User, User	chi-squared test
Prior Anti-TNF DMARD Use	Use	Non-User, User	chi-squared test
Prior Biologic DMARD	Use	Non-User, User	chi-squared test
Number of Prior DMARD Biologics		0, 1, 2, >= 3	chi-squared test
Number of Prior DMARDs (including biologics)		0, 1, 2, >= 3	chi-squared test
Prior Adalimumab	Use	Non-User, User	-
	Reactivity	Response , Inadequate Response, Unknown	-

	Tolerance	Intolerance, Tolerance, Unknown	-
Prior Etanercept	Use	Non-User, User	-
	Reactivity	Response, Inadequate Response, Unknown	-
	Tolerance	Intolerance, Tolerance, Unknown	-
Prior Golimumab	Use	Non-User, User	-
	Reactivity	Response, Inadequate Response, Unknown	-
	Tolerance	Intolerance, Tolerance, Unknown	-
Prior Infliximab	Use	Non-User, User	-
	Reactivity	Response, Inadequate Response, Unknown	-
	Tolerance	Intolerance, Tolerance, Unknown	-
Prior Certolizumab Pegol	Use	Non-User, User	-
	Reactivity	Response, Inadequate Response, Unknown	-
	Tolerance	Intolerance, Tolerance, Unknown	-
Prior Abatacept	Use	Non-User, User	-
	Reactivity	Response, Inadequate Response, Unknown	-

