#### **7.4.1.4 Adjustment for imbalances in demographics and other baseline characteristics**

As for the variables in which imbalance is present in 7.2.2, adjusted analysis will be performed to evaluate the influence.

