#### mTSS change from baseline at Week 28/ET

Rank Analysis of Covariance (RANCOVA) with treatment group (Placebo, ASP015K 100 mg, ASP015K 150 mg) and adjusted variable (if imbalance will be detected) as factor and baseline rank mTSS as covariate.

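### Covariates for the supportive adjusted analyses are selected by significant baseline imbalance instead of being named in advance, and the mTSS model enters them as a factor

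*SAP*

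**What the plan says.** SAP 7.2.2 compares the arms on each listed baseline item, by a continuity-corrected chi-squared test or a one-way ANOVA, in the SAF, FAS and PPS. An adjusted analysis follows on two conditions. The first is statistical: "If the imbalance of the factors between treatment groups is found (at a two-sided 0.05 significance level". The second is clinical: "and considered to clinically affect the primary variable, an analysis adjusted for the factor will be performed".

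SAP 7.4.1.4 restates the rule without the clinical condition: "As for the variables in which imbalance is present in 7.2.2, adjusted analysis will be performed to evaluate the influence". Appendix 1 (the adjusted-analysis row and footnotes 5 and 6) likewise depends on imbalance alone.

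The two models differ. For ACR20, 7.4.1.4 uses a logistic model in which the imbalanced variables are covariates. For mTSS, it uses a rank ANCOVA with treatment and "adjusted variable (if imbalance will be detected) as factor and baseline rank mTSS as covariate".

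SAP 7.1 adds: "Chi-square test is continuity corrected in all analysis".

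Protocol 7.3 plans the baseline tests at 0.05 on the SAF and ties no adjusted analysis to them.

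**The concern.** In a properly randomised trial, a significant baseline difference is a chance event. Its p-value says nothing about how strongly the variable predicts ACR20 response or radiographic progression. A screen on significance therefore adjusts for whatever happened to differ, and never adjusts for a strong predictor that misses 0.05.

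The rule is written before unblinding, but between-arm tests need the treatment codes. The covariates are therefore chosen after the codes are open. Under 7.2.2 the choice also involves a clinical judgement with no stated criterion or decision-maker.

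At stake is the only covariate-adjusted estimate of the ACR20 effect, and the only adjustment of mTSS beyond its own baseline. Neither can serve as a robustness check if its content depends on chance. The mTSS wording adds a second problem: a continuous variable entered as a factor takes one parameter per distinct value.

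**Working it through.** The plan gives no figure for the number of baseline tests or of expected false positives. Its only related figure is the sample size. With difference 2.0 − 0.5 = 1.5, SD 4.0, two-sided 0.05 and 90% power, the two-sample t-test needs 151 per group (power 0.901), as stated. Since 151/0.9 = 167.8, 170 per group is consistent with about 10% dropout. A pairwise mTSS model thus has 2 × 170 = 340 subjects as planned, or 2 × 151 = 302 after dropout.

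**Number of tests.** I counted the rows or items with a named test.
- SAP Table 1, demographics: 8 (for example "Concomitant DMARD except for MTX at Baseline").
- SAP 7.2.2.2, disease activity: 19 items, where "imbalance between treatment groups will be considered based on a one-way ANOVA model with fixed effect for treatment group".
- SAP "Table 2. RA History and Analysis Methods": 13 (8 chi-squared, 5 ANOVA).
- Total: 8 + 19 + 13 = 40. If the 4 WPAI scores and 11 SF-36v2 scores are tested separately, it is 40 − 2 + 4 + 11 = 53.

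**Chance imbalances under valid randomisation.**
- Expected number = k × 0.05. For 40 tests this is 2.0; for 53 it is 2.65. Correlation between tests does not change it.
- P(at least one), independent tests = 1 − 0.95^40 = 0.871. P(at least two) = 0.60.
- Many items overlap (joint counts with DAS28 and SDAI; weight with BMI; mTSS with its components). I simulated 3 × 170 subjects with 40 equally correlated continuous items and 600 repetitions. P(at least one) was about 0.76, 0.59 and 0.42 at assumed correlations of 0.3, 0.5 and 0.7.

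**Cost of class coding in the mTSS model.** Let L be the number of distinct values among n subjects.
- Residual df = n − (L − 1) − 3, the 3 being intercept, treatment and baseline rank mTSS.
- Treatment information retained = [Σ n0·n1/(n0 + n1) over levels] ÷ (n/4). With random allocation this is close to (n − L)/n.

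Results for n = 340, with assumed SDs and recording precision:

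| Variable (assumption) | Levels | Retained | Lost |
|---|---|---|---|
| Age, whole years, SD 12 | about 58 | 0.837 | 16% |
| BMI to 0.1, SD 3.5 | about 130 | 0.619 | 38% |
| Weight to 0.1 kg, SD 10 | 222 | 0.348 | 65% |

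DAS28 to 0.01 (SD 1) is close to the weight row, at 0.344 retained. At n = 302 the three rows retain 0.816, 0.583 and 0.325. RA duration, rounded to one decimal and under 10 years by eligibility, has at most about 100 levels: (340 − 100)/340 = 0.71 retained. Only if every value is unique does the model fail: L = 340 gives residual df = 340 − 339 − 3 = −2 and no information on treatment. Entered as one ranked covariate, any of these costs 1 df and leaves 336.

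**Screening test.** The continuity correction belongs to the 2×2 table. The baseline comparison has three arms, so none of the 11 chi-squared items (3 in Table 1, 8 in Table 2) is 2×2. ACR functional class (3 levels), Steinbrocker stage (4) and the two prior-drug counts (4 each) would not be 2×2 even arm against arm.

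**The case against.** **The clinical condition.** A reader might infer that p < 0.05 alone selects the covariates. Under 7.2.2 it does not, because clinical relevance is also required. The 87% is therefore the chance of any significant test, not of an adjusted analysis being run, and it falls as the items correlate. Some tests can hardly fire: non-MTX DMARDs are prohibited. This stands as a limit on the size of the problem. It does not remove it, since significance is necessary in 7.2.2 and sufficient in 7.4.1.4, and the two sections disagree.

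**The word factor.** It may be loose usage, or may mean the bands that the SAP defines for age, RA duration, CRP and DAS28, at 1 or 2 df each. That is a fair alternative. But the same sentence separates factor from covariate, the ACR20 text says covariate, and height, BMI, onset age, joint counts and HAQ-DI have no baseline bands. For categorical variables, factor is correct.

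**Low impact.** The confirmatory tests in 7.4.1.1 are fixed, and the subgroup analyses in 7.8 examine many prognostic variables whatever their p-values. Both are true. However, subgroup estimates within categories are not an adjusted overall estimate.

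**Protocol 7.3.** It specifies the baseline tests, so deleting them would depart from the protocol. This stands, and the fix keeps them.

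**Conclusion.** The point holds for the supportive adjusted analyses. Their covariates are selected with codes open, from a 40-item screen that yields about 2 chance imbalances on average. P(at least one) is 87% under independence, or about 76% to 42% at assumed correlations of 0.3 to 0.7. Sections 7.2.2 and 7.4.1.4 conflict on the clinical condition, and 7.2.2 does not say which of the three analysis sets triggers adjustment. Baseline mTSS, already in the rank ANCOVA, is itself screened.

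Two stronger readings are not supported. The first is that the primary conclusions are compromised: Fisher's exact test and the rank ANCOVA on baseline rank mTSS do not depend on the screen. The second is that the adjusted mTSS model cannot be estimated: that needs literal class coding and values that are nearly all unique. Otherwise the cost is lost information, about 16% to 65% in the examples, which rest on assumed SDs and recording precision.

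**What to change.** - In 7.4.1.4, name before unblinding a short list of prognostic covariates for each primary endpoint, drawn by the sponsor from the baseline variables already defined in 7.8. Run both adjusted analyses whatever the baseline p-values.
- In the mTSS model of 7.4.1.4 and in Appendix 1 footnote 6, enter continuous variables as covariates (ranked in the RANCOVA) and categorical ones as factors.
- Remove the trigger from 7.2.2, 7.4.1.4 and the Appendix 1 row and footnotes, so that the passages agree.
- Keep the baseline tests of Protocol 7.3 as description only. In 7.1 and 7.2.2, use an uncorrected chi-squared or exact test for tables larger than 2×2.

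The cost is SAP wording and a few more prespecified model runs. The sponsor gives up adjusting for an unexpected imbalance, except in an analysis labelled post hoc.
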